### **9.2.2.1 Incidence of treatment-emergent adverse events**

TEAEs will be presented by SOC and PT. The incidence of TEAE table will include the number and percentage of subjects and number of events by SOC and PT. For the number of subjects by SOC/PT, if a subject experiences the same SOC/PT multiple times during the period, then that PT will only be incremented by one since subject counts will be presented. Percentages will be calculated out of the number of subjects in the SS. The number of events at each level of SOC and PT will also be summarized.

The summary of AEs will be presented in alphabetical order by SOC. Within each SOC, PTs will be sorted by descending order of total frequency (ie, frequency across all study groups). If the total frequency for any two or more PTs is equal within a SOC, the PTs will be presented in alphabetical order.

All TEAEs will be presented in a listing with a glossary.

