12.4 Planned safety analyses

The long-term safety of BRV at individualized doses will be evaluated by means of the safety analyses. Summary tables will be presented over the Evaluation Period as well as Down-Titration Period for all subjects.

All safety variables will be analyzed by descriptive methods on the SS. Treatment-emergent adverse events will be summarized in incidence tables by Medical Dictionary for Regulatory Activities (MedDRA®) Primary System Organ Class and Preferred Term. Separate tables will be provided for AEs leading to withdrawal from the study and SAEs.

Laboratory values, vital signs, and weight will be summarized by period and visit. Possibly clinically significant treatment-emergent abnormalities for laboratory values, vital signs, and weight will be listed and summarized by period and visit. Electrocardiogram abnormalities will also be listed by period and visit.

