## 3 DATA ANALYSIS CONSIDERATIONS

### 3.1 General presentation of summaries and analyses

For the analysis purposes, “core study” in this plan refers to the study where the subjects were firstly enrolled. For rollover subjects, the core study is N01358 (for rollover subjects from N01379) or EP0083 (for rollover subjects from EP0083). For direct enrollers EP0085 is the core study.

Statistical analysis and generation of tables, figures, subject data listings, and statistical output will be performed using SAS® Version 9.3 or higher.

Descriptive statistics will be displayed to provide an overview of the study results. For categorical parameters, the number and percentage of subjects in each category will be presented. The denominator for percentages will be based on the number of subjects appropriate for the purpose of analysis. Unless otherwise noted, all percentages will be displayed to 1 decimal place. No percentage will be displayed for zero counts, and no decimal will be presented when the percentage is 100%.

For continuous parameters, descriptive statistics will include number of subjects with available measurements (n), mean, standard deviation (SD), median, minimum, and maximum. Decimal places for descriptive statistics will always apply the following rules:

- “n” will be an integer.
- Mean, SD and median will use 1 additional decimal place compared to the original data.
- Minimum and maximum will have the same number of decimal places as the original value.

All summaries will be descriptive; no statistical hypothesis testing is planned.

Subject data listings will be provided and will present source data and key derived variables for statistical analyses.

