### **3.5.2        Safety Set**

The Safety Set (SS) will consist of all subjects in the ES who took at least 1 dose of study medication in EP0085. All safety variables will use SS for presentation. In addition,

demographic data, baseline characteristics, medical history, prior and concomitant medications and study drug exposure will use SS for presentation as well.

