## **9 SAFETY ANALYSES**

All safety analysis will be based on SS.

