### **9.2.2 Summaries of TEAEs**

Pre-treatment AEs will be provided in a subject data listing; no summary of pre-treatment AEs are planned. Summaries will be for TEAEs and will be provided overall by combining Evaluation Period, Down-Titration Period, and Study Drug-Free Period unless otherwise indicated.

The following summary of TEAEs will be provided:

- Incidence of TEAEs – overview (overall and by study periods)

The following summaries of TEAEs will be provided by MedDRA SOC and PT:

- Incidence of TEAE (overall and by study periods)
- Incidence of TEAEs by safety time interval (overall)
- Incidence of TEAEs above reporting threshold of 5% of subjects (overall)
- Incidence of non-serious TEAEs above reporting threshold of 5% of subjects (overall)
- Incidence of TEAEs by maximum intensity (overall and by study periods)
- Incidence of TEAEs by relationship (overall and by study periods)
- Incidence of TEAEs leading to permanent discontinuation of study drug (overall)
- Incidence of treatment-emergent SAE (overall and by study periods)
- Incidence of treatment-emergent SAE by relationship (overall)
- Incidence of fatal TEAEs by relationship (overall)
- Incidence of TEAEs of special interest (overall and by study periods)
- Incidence of TEAEs requiring dose change (overall and by study periods)
- Incidence of TEAEs related to COVID-19 vaccination (overall and by study periods)

For by-study period summary tables, TEAEs will be attributed according to the onset date.

Three-month safety time interval will be used to summarize data up to and including the maximum duration of exposure to BRV. TEAEs which had onset prior to or on the date of the last dose of BRV are included in summaries by 3-month time intervals. A subject is included in a 3-month interval if the subject was receiving BRV at any time during that interval based on their duration of exposure to BRV (eg, a subject with exposure for 91 days is included in the time interval for Months 1-3 and Months 4-6). Summaries of AEs by 3-month intervals will include all subjects who are classified into each time interval as defined above as the denominator and TEAEs reported within the specific time interval according to the onset date as the nominator.

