### **9.2.2.3 Serious adverse events**

Serious TEAEs will be presented in a table by SOC and PT in a manner similar to that described in the Section 9.2.2.1. All SAE will be listed by subject.

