### **9.2.2.7 Adverse event requiring dose change**

All TEAEs collected with a study drug action taken as "Dose reduced", "Dose increased" or "Drug temporary interrupted" will be summarized in a table by SOC and PT.

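### By-study-period TEAE percentages rest on the whole Safety Set, so Down-Titration and Study Drug-Free figures fall below incidence among subjects who entered those periods (minor)

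*SAP*

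**What the plan says.** SAP 9.2.2 plans eight TEAE summaries by study period: the overview, all TEAEs, maximum intensity, relationship, serious TEAEs, TEAEs of special interest, TEAEs requiring dose change, and TEAEs related to COVID-19 vaccination. Its only rule specific to these tables concerns the numerator: "For by-study period summary tables, TEAEs will be attributed according to the onset date".

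The percentage base is in SAP 9.2.2.1: "Percentages will be calculated out of the number of subjects in the SS". That sentence follows a rule for counting repeat events within a period. It carries over to other tables by cross-reference, for example in SAP 9.2.2.3: "Serious TEAEs will be presented in a table by SOC and PT in a manner similar to that described in the Section 9.2.2.1". The dose-change section, SAP 9.2.2.7, says only that such events "will be summarized in a table by SOC and PT", and the overview has no base of its own. For those two the only named analysis set is the general one, in SAP 3.5.2 ("All safety variables will use SS for presentation") and SAP 9 ("All safety analysis will be based on SS").

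Two broader statements also bear on this. SAP 3.1: "The denominator for percentages will be based on the number of subjects appropriate for the purpose of analysis". Protocol 12.4: "Summary tables will be presented over the Evaluation Period as well as Down-Titration Period for all subjects".

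**The concern.** A by-period TEAE table is naturally read as saying how often events occurred among subjects who were in that period. With the Safety Set as base, the Down-Titration and Study Drug-Free columns do not say that. They count in the denominator subjects who were never in the period and could not contribute an event to it.

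TEAEs are the primary variable, and these two periods are where events during taper and after stopping appear. The tables are printed by study group. If the share entering a period differs between groups, equal incidence among entrants prints as unequal percentages.

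The 3-month TEAE tables (SAP 3.2.6 and 9.2.2) do not have this feature: their denominator is the subjects on brivaracetam in the interval.

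**Working it through.** **1. Which tables the Safety Set sentence reaches.** Directly: all TEAEs (9.2.2.1). By cross-reference: serious (9.2.2.3), special interest (9.2.2.4), relationship (9.2.2.5), intensity (9.2.2.6) and COVID-19 vaccination (9.2.2.8). That is 6 of 8. The overview and dose-change tables state no base.

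**2. Who is in each period.**
- Evaluation: starts at Visit 1, and dosing starts that evening (Protocol 7.2), so every Safety Set subject is in it.
- Down-Titration: SAP 3.2.5 requires an Early Discontinuation Visit (EDV) and a dose after it.
- Study Drug-Free: SAP 3.2.5 requires a contact after the last dose.
- Converters to commercial brivaracetam enter neither later period (SAP 2.3).

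**3. The factor.** Let k be the subjects with a TEAE whose onset falls in the period. Each of them is an entrant, so k is the same on either base:

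(k / N_entered) / (k / N_SS) = N_SS / N_entered

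For the Evaluation Period N_entered = N_SS and the factor is 1.

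**4. Numbers.** The plan's enrollment figure reproduces: 90 + 7 + 30 = 127 for Japan, and 127 + 90 = 217 in all. I use 217 for N_SS, assuming that everyone enrolled is dosed. The entry share is not in the documents, so it is varied. With k = 10, the Safety Set figure is always 10/217 = 4.6%.

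| Assumed entry | N_entered | 10 / N_entered | Factor 217 / N_entered |
|---|---|---|---|
| 100% | 217 | 4.6% | 1.00 |
| 90% | 195 | 5.1% | 1.11 |
| 75% | 163 | 6.1% | 1.33 |
| 50% | 108 | 9.3% | 2.01 |
| 25% | 54 | 18.5% | 4.02 |

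Put the other way, a 10% incidence among entrants prints as 0.10 × 0.75 = 7.5% at 75% entry and 0.10 × 0.50 = 5.0% at 50%. Two groups with those entry shares and identical incidence would show 7.5% and 5.0%.

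In a small column the choice of base is also a matter of stability. With 30 planned direct enrollers, one subject with an event is 1/30 = 3.3% on the Safety Set and 1/15 = 6.7% if 15 entered.

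**5. Counting entrants to Down-Titration.** Two parts of SAP 3.2.5 do not agree:
- The Evaluation Period rule covers completed subjects who enter Down-Titration, and ends their Evaluation Period at the End of Study Visit.
- The Down-Titration rule admits only subjects with an EDV, and says that a subject without one has no such period.

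Read literally, a completer who tapers after an End of Study Visit has no Down-Titration Period. The Evaluation Period then runs to the last dose, and any TEAE during the taper is attributed to Evaluation. Protocol 5.1 provides for down-titration after completion as well as after early discontinuation, so the case is foreseen.

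**The case against.** The strongest reply is that the Safety Set base is a legitimate, stated convention. Protocol 12.4 asks for Evaluation and Down-Titration tables covering all subjects and puts safety analyses on the Safety Set, and the SAP writes a different denominator where it wants one. Share of all treated and share of entrants answer different questions; entry is itself a post-baseline event, and no document names the second as the target. This stands in part: a share of all treated is a valid quantity if it is labelled as such. But Protocol 12.4 sets an analysis set rather than a percentage base, and it does not mention the Study Drug-Free Period.

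A second reply is that SAP 3.1 already allows a suitable denominator. It does not rule out a period-specific N, but it names none, and the specific sentence in 9.2.2.1 points the other way.

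A third is that little turns on this. The study is noncomparative and descriptive, subject and event counts are printed, all TEAEs are listed, and SAP 5.1 reports the number starting each period by study group. That stands, and it is why the point is minor. A reader can recompute from the disposition table, although for Down-Titration the count depends on which reading of 3.2.5 is used.

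On 3.2.5, EDV may be shorthand for either visit: the protocol gives the two visits one schedule column and one assessment list (Tables 5-1 and 5-2, section 8.7). That is plausible, but the SAP does not say so, and elsewhere in the same section it separates the two visits.

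**Conclusion.** The point holds and is minor. As the SAP is written, TEAE percentages for Down-Titration and Study Drug-Free are shares of all treated subjects and lie below incidence among entrants by N_SS/N_entered. The identity is exact. Its size is unknown, because every entry share used here is an assumption. Overall tables and subject counts do not change.

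A reader might infer more than the documents support:
- That the plan gives no base for by-period tables. For six of the eight it does: the Safety Set.
- That the primary safety result is biased, or that taper-phase events are hidden. The overall tables correctly use the Safety Set, and the counts and listing show every event.
- That the dilution is large. Nothing in the documents says how many subjects enter either period, and the factor is 1 if all do.
- That completers' taper-phase TEAEs will certainly be placed in the Evaluation Period. That follows only if EDV in 3.2.5 is read literally.

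**What to change.** In SAP 9.2.2.1, state that percentages in by-study-period tables, including the overview and dose-change tables, are based on Safety Set subjects who entered that period under Section 3.2.5, with that number shown as N in the column header, and that overall tables keep the Safety Set. If a share of all treated subjects is what is wanted, say so in the table title and print the number who entered beside it.

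In SAP 3.2.5, reconcile the Down-Titration entry definition with the provision for completed subjects who enter after an End of Study Visit, so that both their taper-phase TEAEs and their place in N are assigned to Down-Titration.

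The cost is SAP wording and minor table programming; the numbers starting each period are already planned for the disposition table, and no new data are needed. The downside is that Down-Titration and Study Drug-Free percentages will rest on smaller, less stable denominators and will print slightly less favourably.

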### **9.2.2.2 Withdrawal due to adverse events**

All TEAEs collected with a study drug action taken as “Drug permanently withdrawn” will be summarized in a table by SOC and PT in a manner similar to that described in the Section 9.2.2.1. All AE leading to study discontinuation or permanently withdrawal of study drug will be listed by subject.

### **9.2.2.3 Serious adverse events**

Serious TEAEs will be presented in a table by SOC and PT in a manner similar to that described in the Section 9.2.2.1. All SAE will be listed by subject.

### **9.2.2.4 Adverse events of special interest**

The following AEs are considered as AEs of special interest:

- autoimmune nephritis
- nephritis
- nephritis allergic
- tubulointerstitial nephritis
- uveitis syndrome
- Potential Hy's Law

The TEAE of special interest, which will be captured on the CRF page, will be categorized and presented by SOC and PT in a manner similar to that described in the Section 9.2.2.1.

### **9.2.2.5 Relationship of adverse events to study drug**

The relationships of TEAE will be either “Related” or “Not Related” according to the CRF entry. AEs with missing relationship will be presented in the summary table as “Related” but will be presented in the data listing with a missing relationship.

The AE data will be categorized and presented by SOC and PT in a manner similar to that described in the Section 9.2.2.1.

### **9.2.2.6 Intensity of adverse event**

Summary of TEAEs will be presented by maximum intensity:

In the TEAE by maximum intensity table, if a subject experiences multiple occurrences within the SOC and PT during that period, the subject is counted only once according to the maximum intensity within that SOC or PT (severe > moderate > mild).

AEs with missing intensity will be presented on tables as “Severe” but will be presented in the data listing with a missing intensity.

The AE data will be categorized and presented by SOC and PT in a manner similar to that described in the Section 9.2.2.1.

### **9.2.2.7 Adverse event requiring dose change**

All TEAEs collected with a study drug action taken as "Dose reduced", "Dose increased" or "Drug temporary interrupted" will be summarized in a table by SOC and PT.

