3 STUDY OBJECTIVES

3.1 Primary objective

The primary objective is to evaluate the long-term safety and tolerability of BRV in focal epilepsy subjects with partial seizures.

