5 STUDY DESIGN

5.1 Study description

EP0085 is a Phase 3, open-label, LTFU, multicenter, noncomparative, and dose flexible study to be conducted in Japan and China. The population will be subjects (≥ 16 years of age) with partial seizures with or without secondary generalization. Subjects of a minor age are included only where legally permitted and ethically accepted. In Japan, subjects meeting the inclusion and exclusion criteria as specified in Section 6.1 may be directly enrolled. Rollover subjects must complete the Treatment and Transition Period of EP0083 prior to enrollment into EP0085.

In addition, Japanese subjects participating in N01379, the long-term open-label extension to the Phase 3, placebo-controlled study N01358, may enter this study. Upon completion or early discontinuation from EP0085, there will be a Down-Titration Period, followed by a 2-week Study Drug-Free Period during which the subject will not receive study drug.

Directly enrolled subjects in Japan and rollover subjects from EP0083 will be started on oral BRV at a dose of 100mg/day (2 equally divided doses administered twice daily) at study entry and should be maintained at this dose for at least 2 weeks, unless the subject is unable to tolerate treatment.

Japanese subjects from N01379 can enter EP0085 at a dose up to 200mg/day. After Visit 1, the next visit for subjects entering from N01379 will be Visit 4 (Visit 2 and Visit 3 will not be conducted). Subsequent visits will be conducted according to the visit schedule provided in Table 5-3. The BRV dose can be adjusted based on the individual subject's seizure control and tolerability between 50mg/day and 200mg/day during the study and must always be administered as a symmetrical morning and evening dose except the last week of down-titration. Of note, decreasing the dose should not exceed 50mg/day. Study medication in the last week of down-titration is given only in the morning.

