10 ASSESSMENT OF SAFETY

10.1 Adverse events

10.1.1 Definitions

10.1.1.1 Adverse event

An AE is any untoward medical occurrence in a patient or clinical investigation subject administered a pharmaceutical product that does not necessarily have a causal relationship with this treatment. An AE can therefore be any unfavorable and unintended sign (including an abnormal laboratory finding), symptom, or disease temporally associated with the use of a medicinal (investigational) product, whether or not related to the medicinal (investigational) product.

In order to ensure complete safety data collection, all AEs occurring during the study (ie, after the signing of the ICF), including any pretreatment and posttreatment periods required by the protocol, must be reported in the eCRF even if no IMP was taken but specific study procedures were conducted. This includes all AEs not present prior to the initial visit and all AEs that recurred or worsened after the initial visit.

Signs or symptoms of the condition/disease for which the IMP is being studied should be recorded as AEs only if their nature changes considerably or their frequency or intensity increases in a clinically significant manner as compared to the clinical profile known to the Investigator from the subject's history or the Baseline Period.

For results disclosure on public registries (eg, ClinicalTrials.gov), TEAEs and treatment-emergent SAEs will be published.

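### SAP 9.2.2.7 counts dose increases together with dose reductions and interruptions, so its overall and SOC totals cannot show how often TEAEs limited dosing

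*SAP*

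**What the plan says.** SAP 9.2.2.7 defines the table: "All TEAEs collected with a study drug action taken as 'Dose reduced', 'Dose increased' or 'Drug temporary interrupted' will be summarized in a table". Its rows are SOC and PT, and no column or sub-row for the action is described. SAP 9.2.2 lists the matching output as a single item, "Incidence of TEAEs requiring dose change (overall and by study periods").

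Permanent withdrawal is handled apart from this. SAP 9.2.2.2 states: "All TEAEs collected with a study drug action taken as “Drug permanently withdrawn” will be summarized in a table by SOC and PT".

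Two protocol sections bear on what the pooled actions mean. Protocol 5.1 states: "The BRV dose can be adjusted based on the individual subject's seizure control and tolerability between 50mg/day and 200mg/day during the study". Protocol 10.1.1.1 says that signs or symptoms of the disease under study "should be recorded as AEs only if their nature changes considerably or their frequency or intensity increases in a clinically significant manner". The primary objective (Protocol 3.1) is to "evaluate the long-term safety and tolerability of BRV" in subjects with partial seizures.

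**The concern.** A reduction or an interruption because of a TEAE means that the event limited dosing. An increase alongside a TEAE moves in the opposite direction, and in a dose-flexible epilepsy study one plausible reason is that seizures worsened. Once the actions share one count, the total rises in both situations.

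At stake is how one descriptive table can be read. With tolerability in the primary objective, a reader will want to know how often a TEAE limited dosing without ending treatment. No other planned summary gives that number. A reader comparing study groups in this table could not tell more intolerance from more up-titration after seizure worsening.

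**Working it through.** The plan states no figure for this table, so there is nothing to reproduce. The check is mainly one of text.

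**Step 1: what is pooled.** SAP 9.2.2.7 names three actions, and SAP 9.2.2 lists one output for them. Neither says that the action, or the direction of the dose change, will be shown.

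**Step 2: can a dose-increase TEAE arise from insufficient effect?** Protocol 5.1 gives seizure control and tolerability as the two grounds for adjusting the dose. Rollovers from EP0083 and direct enrollers start at 100mg/day within a range of 50 to 200mg/day, so there is room to go up. Protocol 10.1.1.1 admits marked seizure worsening as an AE. A seizure-worsening TEAE with the dose increased is therefore a foreseeable record. Neither section says that every such record has this cause.

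**Step 3: is the split available elsewhere?**
- SAP 9.2.2.2 covers permanent withdrawal only.
- SAP 5.4 analyses time to discontinuation separately for TEAE, for lack of efficacy, and for either. It draws the relevant distinction, but only for stopping treatment.
- SAP 9.1.2 summarizes mean and modal daily dose, without reasons for changes.
- SAP 9.2.2 lists a TEAE overview without itemizing its lines.
- SAP 9.2.2.1 lists all TEAEs by subject, but does not say that action taken is displayed.

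No planned summary supplies the split.

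**Step 4: what the total can and cannot tell.** Let r be the percentage of subjects with a reduction or interruption TEAE, i the percentage with a dose-increase TEAE, and o the percentage with both. The table reports

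P = r + i − o.

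P alone leaves r anywhere between 0 and P. The same holds for any SOC total containing both kinds of event. Within a PT row, the two mix only if both kinds of action were taken for that term.

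**Step 5: illustration under assumed rates.** The documents give neither r nor i. Assume r = 5% to 20%, i = 1% to 5% and o = 0. The share of counted subjects who are there because of an increase is i/(r + i):

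| r | i | P = r + i | i/(r + i) |
|---|---|---|---|
| 20% | 1% | 21% | 1/21 = 4.8% |
| 5% | 1% | 6% | 1/6 = 16.7% |
| 20% | 5% | 25% | 5/25 = 20% |
| 5% | 5% | 10% | 5/10 = 50% |

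With the planned 217 subjects (SAP 2.4), r spans about 11 to 43 subjects (0.05 × 217 = 10.9; 0.20 × 217 = 43.4), and i about 2 to 11 (0.01 × 217 = 2.2; 0.05 × 217 = 10.9). Any overlap (o > 0) lowers the share of subjects counted only because of an increase, (i − o)/P.

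**The case against.** The strongest reply is that the table does what its name says. The SAP calls it TEAEs requiring dose change, and an increase is a dose change. A reader might infer that this is the plan's tolerability table and that it is therefore mis-specified. The documents do not support that: no section designates it as the tolerability measure, and Protocol 12.4 asks for separate tables only for SAEs and for AEs leading to withdrawal, both of which are planned. This stands, and it means the point is about missing information, not about an error or contradiction.

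A reader might also infer that every dose increase signals poor seizure control. No section says so. Ordinary up-titration for incomplete control produces no TEAE under Protocol 10.1.1.1 and never reaches the table. Some of the worsening that does qualify may instead lead to withdrawal under Protocol 6.3, and TEAEs with the drug permanently withdrawn are tabulated elsewhere. These routes suggest that the number of dose-increase TEAEs may be small, but they do not exclude them.

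The PT rows keep seizure terms apart from terms such as somnolence or dizziness, so the mixing sits mainly in the any-TEAE line and the SOC totals. This stands too and narrows the point.

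Finally, listings present source data (SAP 3.1), so the split is probably recoverable subject by subject. The SAP does not promise that action taken appears there, and in any case a listing is not a summary.

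**Conclusion.** The point holds in a limited form. The any-TEAE and SOC totals of the dose-change table cannot show how often TEAEs limited dosing short of permanent withdrawal, and no other planned summary can. The PT rows give partial separation.

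The size is unknown. The 4.8% to 50% range rests wholly on assumed rates and on no subject having both kinds of action; it shows that the mix could be negligible or substantial and is no estimate for this trial. The conclusion also assumes that some dose-increase TEAEs reflect seizure worsening, which the protocol makes plausible but does not state.

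Consequences are minor. SAP 3.1 makes all summaries descriptive, and no hypothesis test depends on this table. It is an optional improvement, worth making because tolerability is in the primary objective and SAP 5.4 already separates TEAE from lack of efficacy for discontinuation.

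**What to change.** In SAP 9.2.2.7, present the table by action taken, with *dose reduced or temporarily interrupted* separate from *dose increased*, by SOC and PT, overall and by study period. Amend the corresponding item in SAP 9.2.2 to match. Add the reduced-or-interrupted line to the TEAE overview, so that the number and percentage of subjects whose dosing was limited by a TEAE can be read directly. The pooled line can stay as a total. A subject with both kinds of action should count once in each part and once in the total, with a footnote saying so.

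The cost is one table split and one overview line. SAP 9.2.2.7 already relies on the recorded action, so no new data are needed, and no dosing or other clinical rule changes.
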